#### 5. SAMPLE SIZE DETERMINATION

Approximately 125-140 patients are expected to be enrolled in this study (approximately 30-50 patients in Part 1 and 87-102 patients in Part 2).

The exact sample size of the mTPI design in Part 1 cannot be pre specified in advance because it is a dynamic feature of the design. The maximum sample size after which the Part 1 will be stopped and MTD declared is 30-50 patients. Also, a minimum of 9 patients is required to establish the MTD. The actual sample size of Part 1 will depend on the underlying dose toxicity profile and variability in actual data realization.

As for the number of patients treated at each dose, it is expected that the typical number will be 2 to 4 patients for the doses actually studied. For the dose declared as the MTD from Part 1, a minimum of 9 patients will be observed at this dose to further investigate the anti-leukemic activity, safety, and PK profile of PF-06747143. However, since not every dose listed will be studied and variable cohort size is allowed, the actual number of patients treated at each dose will vary.

#### 6. ANALYSIS SETS

Several analysis sets are defined and will be considered for this study.

#### 6.1. Full Analysis Set

The full analysis set includes all enrolled patients. This is equivalent to the ITT (intent-to-treat) population.

#### 6.2. 'PER PROTOCOL' Analysis Set

The per protocol analysis set includes all enrolled patients who receive at least one dose of study treatment at the dose level of MTD and who do not have major treatment deviations during first cycle. Patients with major treatment deviations in Cycle 1 are not evaluable for the MTD assessment and may be replaced. Major deviations include failure to satisfy major entry criteria (eg, confirmation of the target disease population; signed informed consent), administration of less than 3 out of the 4 doses in Cycle 1 or 80% of the planned Cycle 1 dose (provided that the reduction is not due to toxicity attributable to PF-06747143) or use of

other anti-cancer/anti-leukemia treatments during the active treatment and disease follow up phases other than as defined/allowed in this protocol.

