#### 2.2.2.3. MTD Definition

In Part 2, the MTD of the combinations of PF-06747143 and intensive daunorubicin/cytarabine or PF-06747143 and decitabine/azacitaditine will be determined separately within each cohort.

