#### 4.2. Statistical Decision Rules

#### 4.2.1. Part 1

Decision rules are based on calculating unit probability mass (UPM) of three dosing intervals corresponding to under, proper, and over dosing in terms of toxicity. Specifically, the underdosing interval is defined as (0; pT-e1), the over-dosing interval (pT+e2), and the proper-dosing interval (pT-e1, pT+ e2), where e1 and e2 are small fractions. For a target DLT rate of 0.25, the target equivalence interval is (0.20, 0.30). The three dosing intervals are associated with three different dose-escalation decisions (Table 1). The under-dosing interval corresponds to a dose escalation (E), over-dosing corresponds to a dose de-escalation (D), and proper-dosing corresponds to remaining at the current dose (S). Given a dosing interval and a probability distribution, the unit probability mass (UPM) is defined as the ratio of the probability of the interval to the length of the interval. Once the safety assessment is complete for Cycle 1, the focus will be on allocation of new subjects to the dose most likely to be an MTD.

The study continues accruing until one of the three stopping conditions below is triggered. The algorithm will stop if any of the following criteria is met:

- 1. The maximum sample size has been achieved.
- 2. MTD has been identified with sufficient accuracy: at least 9 patients have been accumulated on a dose that is currently estimated to be the MTD, or
- 3. All doses explored appear to be overly toxic and the MTD cannot be determined.

Specifically the mTPI approach formalizes stopping rules as follow:

Rule 1 (early termination): if the first dose is too toxic  $\rightarrow$  Pr( $p_1 > p_T / data$ ) >  $\xi$  ;  $\xi = 0.975$ 

Rule 2 (dose exclusion), if dose= i is too toxic  $\rightarrow$  Pr( $p_i > p_T / data$ ) >  $\xi$  ;  $\xi = 0.975$  then exclude doses  $\geq i$ 

#### 4.2.2. Part 2

Part 2 of this study is intended to confirm the safety and tolerability of the dose selected in Part 1 while assessing the anti-leukemia activity of PF-06747143 in combination with standard dose of intensive chemotherapy. The DLT rate and its 95% confidence interval at the selected dose may be estimated. Part 2 data will also be used to determine the safey of combining PF-06747143 with standard chemotherapy in addition to justifying the efficacy of PF-06747143 monotherapy.

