#### 9.2. Statistical Analyses

#### 9.2.1. Primary Analysis

Dose Limiting Toxicity (DLT) is the primary endpoint of the dose escalation component of the study, which will be summarized by dose level using the Per Protocol Analysis Set for patients in the dose escalation portion of the study. A listing of the DLTs will also be provided.

If necessary, a summary and listing of the DLT by malignancy may be provided using the Per Protocol Analysis Set for patients in the MTD expansion portion of the study.

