#### 9.2.2. Secondary Analyses

#### 9.2.2.1. Efficacy Analysis

In this Phase 1 study efficacy is a secondary objective. Note that the efficacy analysis is to be conducted by malignancy for patients in the MTD expansion cohorts who are in the Safety Analysis Set and have baseline disease assessment and at least one post-baseline disease assessment. In the event that a large number of patients in the escalation portion of the study have the same malignancy, the efficacy analysis may be conducted.

Summary tables of best Overall Response Rate, Progression Free Survival, and Overall Survival will be provided overall and by malignancy. Efficacy listings will be provided that include best response, first CR/PR date, last date with CR or PR, most recent date without progression, progression date, death date, date of first response and last tumor assessment date, etc.

A response rate overall for Part 1 dose escalation and response rates by low, medium, and high dose groups may be presented.

The following table provides an overview of the efficacy analysis.

**Endpoint Analysis Set** Interpretation **Statistical** Model/ Missing Method Covariates/ Data Strata By dose range/ Overall Per Protocol, Exact CI Censored Secondary response expansion malignancy per Section Analysis 11.2 cohorts, etc. Progression Per Protocol, Kaplan-By malignancy Censored Secondary Free Survival expansion per Section Meier Analysis (PFS) cohorts 11.2 Per Protocol, By malignancy Censored Secondary Time to Kaplan-Progression expansion Meier per Section Analysis cohorts 11.2 (TTP) Duration of Per Prtocol, By malignancy Censored Secondary Kaplan-Response (DR) expansion Meier per Section **Analysis** cohorts 11.2

**Table 2.** Overview of Efficacy Analysis

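### The Per Protocol set admits only patients dosed at the MTD, yet the Part 1 primary DLT table is to be shown by dose level in that set

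*SAP*

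**What the plan says.** Section 6.2 defines the Per Protocol set as "all enrolled patients who receive at least one dose of study treatment at the dose level of MTD", provided they have no major treatment deviation in the first cycle. The next sentence gives a purpose that is not tied to one dose: "Patients with major treatment deviations in Cycle 1 are not evaluable for the MTD assessment and may be replaced".

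Section 9.2.1 names DLT as the primary endpoint of dose escalation, "which will be summarized by dose level using the Per Protocol Analysis Set for patients in the dose escalation portion of the study". It adds a DLT listing and, if needed, a DLT summary in the same set for the MTD expansion portion. No other analysis set is named for DLT, and Section 6 defines no DLT-evaluable set.

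Section 4.2.1 allows Part 1 to stop without an MTD: "All doses explored appear to be overly toxic and the MTD cannot be determined". Section 5 says that "a minimum of 9 patients is required to establish the MTD" and expects about 30 to 50 patients in Part 1.

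For efficacy, the text of Section 9.2.2.1 analyses patients in the "MTD expansion cohorts who are in the Safety Analysis Set and have baseline disease assessment and at least one post-baseline disease assessment". Table 2 in the same section assigns overall response, PFS, time to progression and duration of response to the Per Protocol set and the expansion cohorts, with response also broken down by dose range. Section 2.2.2.3 says that the MTD of each combination "will be determined separately within each cohort".

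**The concern.** A set restricted to one dose level cannot support a table by dose level. The definition is also circular. Section 7.2.2 picks the MTD in practice as the highest dose with a DLT rate of at most 33%, which requires DLT rates at several doses. Yet membership of the set that reports those rates depends on the MTD already being known.

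What is at stake is the reported primary analysis of Part 1. A reader needs DLT counts and denominators at each dose to see how toxicity changes with dose and why the MTD was chosen. Under the written definition, those figures appear only for the MTD. If every dose proves too toxic, the table is blank in the very case where DLT data matter most. For efficacy, the text and Table 2 give different denominators for the same response rate.

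**Working it through.** The SAP gives no size for the Per Protocol set, so there is no planned figure to reproduce. The check compares the sections and then sizes the loss from the plan's own counts.

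**Step 1: who can enter the set.** Section 2.1.1.2 (Table 1) plans six dose levels and bars intra-patient escalation.
- Patients who start below the MTD never receive the MTD dose, so they are out.
- Patients who start above the MTD qualify only if later reduced to it, and would then be a selected few.
- Patients who start at the MTD qualify if they have no major Cycle 1 treatment deviation.

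The by-dose table therefore has, in essence, 1 of 6 planned rows. Under the third stopping criterion of Section 4.2.1 it has none.

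**Step 2: share of Part 1 patients left out.** Let n be the patients at the MTD and N the Part 1 total. Excluded share = 1 − n/N = (N − n)/N, assuming no other exclusions. N is 30 to 50 (Section 5). The minimum n is 9 (Section 5); 12 and 15 are assumed, to show the range.

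| n at MTD | N = 30 | N = 50 |
|---|---|---|
| 9 | 21/30 = 70% | 41/50 = 82% |
| 12 | 18/30 = 60% | 38/50 = 76% |
| 15 | 15/30 = 50% | 35/50 = 70% |

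**Step 3: simulation, indicative only.** The Appendix 3 decision rules were simulated with cohorts of 3 and six dose levels, stopping at 9 patients on the dose next assigned or at 50 in total, with 20,000 runs per scenario. The DLT rate was set at 25% at the true MTD. Rates at the other doses are assumptions, since the SAP gives none.
- Mean share excluded: 48%, 55%, 59% and 62% for a true MTD at 3, 10, 15 and 20 mg/kg. Across other assumed curves the range for these four doses was 42% to 64%.
- For a true MTD at 0.3 or 1.0 mg/kg the loss was smaller, about 20% to 35%.
- Mean N was 19 to 25 in the runs behind the 48% to 62% figures, below the planned 30 to 50. For a fixed n, a larger N excludes more, which is why Step 2 gives higher figures.
- Stopping with no MTD was uncommon: at most about 7% of runs, with the true MTD at the lowest dose.

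**Step 4: efficacy.** The combination cohorts start at 10 mg/kg and may move up or down (Sections 2.2.1, 2.2.2.1 and 2.2.2.2).
- If the text of Section 9.2.2.1 governs, the MTD restriction has no effect, but treated patients without both a baseline and a post-baseline assessment drop out.
- If Table 2 governs and MTD means each combination's own MTD, most patients stay in.
- If Table 2 governs and MTD means the single-agent MTD, every combination patient not treated at that dose drops out. That could be a whole expansion cohort of up to 30.

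The SAP does not say which reading applies. Table 2's response by dose range is also impossible in a set confined to one dose.

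**The case against.** The strongest reply is that this is a drafting slip with a recoverable intent and limited consequences. Much of that is true.
- The mTPI decisions use all patients treated at the same dose level (Section 2.1.1.2), not the Per Protocol set. Dose allocation is untouched, and there is no hypothesis test to distort.
- Sections 6.6 and 7.2.1 describe evaluability with no dose restriction. Together with the by-dose display in Section 9.2.1, they suggest that a set across all doses was meant.
- A DLT listing is planned with no analysis set named, so cases at other doses may still be listed. AE and laboratory summaries in the Safety Analysis Set cover every dose.
- Section 7.2.2 also defines the MTD as any dose with a true DLT probability of 20% to 30%, so more than one level might qualify. Section 5 says that not every listed dose will be studied.

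These points narrow the consequence but do not remove it. The evaluability rules are not tied to Section 9.2.1, and whoever derives the population flag works from the definition in Section 6.2. A listing gives no denominators, and AE tables do not count DLTs in evaluable patients. Dose levels outside the 20% to 30% interval still drop out. It is also fair that the simulated figures depend on assumed rates and that the efficacy part is conditional. The contradiction between Sections 6.2 and 9.2.1 rests on neither.

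**Conclusion.** The point holds and should be corrected before analysis. As written, the analysis set for the Part 1 primary endpoint defeats the display that the SAP prescribes for it: essentially one dose level is shown, and none if no MTD is found. By the plan's own counts, 70% to 82% of Part 1 patients are excluded with 9 at the MTD, falling to 50% to 70% with an assumed 15. Simulation under assumed dose-toxicity curves puts the mean loss at 42% to 64% for a true MTD at 3 mg/kg or above, and at 20% to 35% for the two lowest doses. The fault lies in the reported DLT analysis, not in dose escalation. The efficacy conflict is also real, but its size cannot be fixed until the SAP says which set, and which MTD, applies.

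**What to change.** 1. In Section 6.2, delete the restriction to the MTD dose level. Alternatively, and more clearly, define a DLT-evaluable set: treated Part 1 patients at any dose level who either have a DLT or complete the DLT window without a major Cycle 1 deviation. Align it with Section 7.2.1, including the 28-day requirement and the patients whom the investigators and sponsor agree to count as evaluable. Deleting the phrase alone would leave those rules outside Section 6.2.
2. Name that set in Section 9.2.1 for the by-dose DLT summary. If an MTD-level subset is wanted for the expansion portion, define it separately.
3. Reconcile Table 2 with the text of Section 9.2.2.1 by naming one efficacy set for each expansion cohort that does not depend on the MTD dose level. If the subset with baseline and post-baseline assessments is kept, report how many treated patients it leaves out.

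The cost is SAP wording only, with no new data. The protocol is not at hand; if it carries the same definition, it should be brought into line.

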#### PK analysis sets

The PK parameter analysis population is defined as all enrolled patients treated who have sufficient information to estimate at least 1 of the PK parameters of interest. The PK concentration population is defined as all patients who receive PF-06747143, have no major deviations affecting the PK assessment, and have at least one post-dose concentration measurement.

#### 6.3. Safety Analysis Set

The safety analysis set includes all enrolled patients who receive at least one dose of study medication.

#### **6.4. Other Analysis Sets**

#### **6.4.1. Modified Intent-to-Treat Set**

The modified intent-to-treat (mITT) is the analysis population that will follow the ITT principle and include subjects receiving at least 1 dose of study medication with baseline assessment and at least 1 post baseline assessment or disease progression or death before the first assessment. The mITT population may be used for interim analysis and conference presentations when the study is still ongoing.

#### 6.5. Treatment Misallocations

Subjects who receive the wrong initial dose for whatever reason will be analyzed according to the initial dose actually received. Subjects who receive the wrong dose after the initial dose will be analyzed according to the initial dose received.

#### 6.6. Protocol Deviations

All deviations will be listed in the CSR. Major treatment deviations include, but are not limited to, less than 80% of the planned Cycle 1 PF-06747143 dose provided the reduction/omission is not due to treatment-related toxicity. Subjects with major Cycle 1 treatment deviations are not evaluable for MTD.

#### 7. ENDPOINTS AND COVARIATES

#### 7.1. Efficacy Endpoint(s)

Preliminary evidence of anti tumor activity including objective disease response; as assessed using the standardized response criteria for the hematologic disease under study including objective response rate (ORR), duration of ORR, time to progression (TTP) and progression free survival (PFS).

The above efficacy endpoints are derived based on the disease response per investigator evaluation on the CRF pages, which is the primary method of documentation of disease:Overall Response (OR) – Preliminary evidence of anti-leukemia activity including objective disease response will be assessed using the standardized response criteria, as recommended by an international expert panel, on behalf of the European LeukemiaNet (Dohner, et. al 2010), including objective response rate (ORR), duration of ORR, and relapse free survival (RFS) (section 7.6) All measurable disease must be documented at screening and re assesses at each subsequent tumor evaluation. Overall response is the best response recorded from first dose until disease progression/recurrence and it must include confirmation. To be assigned a status of PR or CR, changes in leukemia measurements must be confirmed by repeat assessments that should be performed no less than 4 weeks after the criteria for response are first met.

**Progression Free Survival (PFS)** - is defined as the time from Cycle 1 Day 1 (C1D1) to first documentation of disease progression or to death due to any cause, whichever occurs first. Subjects last known to be 1) alive 2) on treatment or within the post-treatment follow-up period and 3) progression-free, are censored at the date of the last disease assessment that verified lack of disease progression. Subjects who start new anti-cancer treatment prior to the end of post-treatment follow-up period and have adequate baseline and on-treatment objective disease assessments without evidence of progressive disease are censored at the date of the last objective disease assessment. Subjects with inadequate baseline or no on-study disease assessments are censored at C1D1 unless death occurred prior to the first planned assessment (in which case the death is an event). Subjects with at least one on-study disease assessment who discontinue treatment without disease progression and without death within 28 days of discontinuation are censored at the date of the last objective disease assessment that verified lack of disease progression (if progression or death is within 28 days of discontinuation the progression or death is an event). Subjects with documentation of progression or death after an unacceptably long interval (>16 weeks) since the previous disease assessment will be censored at the time of the previous assessment.

PFS (days) = [progression/death date - C1D1 + 1].

• Overall survival (OS) is defined as the time from initial dose until death from any cause, and is measured in the intent-to-treat population.

More details of censoring are provided in Appendix 2.

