#### 11.2. APPENDIX 2: CENSORING DETAILS

Table 4. Progression Free Survival and Duration of Response

Situation	Date of Progression/Censoring 	Outcome		
Inadequate baseline assessment	Start date (C1D1)	Censored		
No on-study assessments	Start date (C1D1)	Censored		
Alive, on treatment  and no Progression	Date of last objective tumor assessment	Censored		
Progression Documented on or between scheduled tumor assessments prior to treatment discontinuation 	Date of first objective tumor assessment showing objective progression	Progressed (Event)		
Treatment discontinuation for undocumented progression	Date of last objective tumor assessment prior to discontinuation 	Censored		
Treatment discontinuation due to toxicity or other reason	Date of last objective tumor assessment prior to discontinuation 	Censored		
Death prior to first planned tumor assessment	Date of death	Death (Event)		
Death without objective progression prior to treatment discontinuation 	Date of death	Death (Event)		
Death or progression after 2 or more missed tumor assessments	Date of last objective tumor assessment prior to the event	Censored		

1: For date of censorship, if a tumor assessment takes place over a number of days (eg, superficial lesions one day, scans another), the last date is used as the assessment date.

**Table 5.** Time to Progression

Situation	Date of Progression/Censoring 	Outcome		
Inadequate baseline assessment	Start date (C1D1)	Censored		
No on-study assessments	Start date (C1D1)	Censored		
Alive, on treatment  and no	Date of last objective tumor assessment	Censored		
Progression	-			
Progression Documented on or	Date of first objective tumor assessment	Progressed (Event)		
between scheduled tumor assessments	showing objective progression			
prior to treatment discontinuation 				
Treatment discontinuation for	Date of last objective tumor assessment	Censored		
undocumented progression	prior to discontinuation 			
Treatment discontinuation due to	Date of last objective tumor assessment	Censored		
toxicity or other reason	prior to discontinuation 			
New anticancer treatment <28 days	Date of last objective tumor assessment	Censored		
after discontinuation of treatment	prior to new anticancer treatment			
without progression				
Death prior to first planned tumor	Start date (C1D1)	Censored		
assessment				

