Death without objective progression	Date of last objective tumor assessment	Censored		
prior to treatment discontinuation 	prior to death			
Progression after 2 or more missed	Date of last objective tumor assessment	Censored		
tumor assessments	prior to the event			

1: For censoring date, if a tumor assessment takes place over a number of days (eg, superficial lesions one day, scans another), the last date is used as the assessment date.

2: or within 28 days of discontinuation of treatment.

2: or within 28 days of discontinuation of treatment.

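### The PFS rules both censor at Day 1 and count as an event a never-assessed patient who dies after the first planned assessment, with no precedence stated

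*SAP*

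**What the plan says.** SAP Section 7.1 defines PFS as the time from Cycle 1 Day 1 (C1D1) "to first documentation of disease progression or to death due to any cause, whichever occurs first". The censoring text that follows says: "Subjects with inadequate baseline or no on-study disease assessments are censored at C1D1 unless death occurred prior to the first planned assessment". A separate sentence makes a death within 28 days of discontinuation an event, but it concerns "Subjects with at least one on-study disease assessment who discontinue treatment without disease progression and without death within 28 days of discontinuation".

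Sections 7.1 and 8.2 both refer to Appendix 2 (Section 11.2) for the detail. Four rows of Table 4 there matter:

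- "No on-study assessments": start date (C1D1), censored.
- "Death prior to first planned tumor assessment": date of death, event.
- "Death without objective progression prior to treatment discontinuation": date of death, event. Footnote 2 widens this row with "or within 28 days of discontinuation of treatment".
- "Death or progression after 2 or more missed tumor assessments": last objective assessment before the event, censored.

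Neither Section 7.1 nor Appendix 2 says which row prevails when two apply, or whether the table or the text governs.

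**The concern.** Consider a patient who starts treatment, misses the first planned disease assessment, and dies shortly afterwards while on treatment or within 28 days of stopping. No progression was documented and no on-study assessment exists. The SAP gives this patient two opposite outcomes, so two programmers could both follow it faithfully and produce different PFS data.

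The choice is not neutral. Under Day 1 censoring the patient leaves every later risk set, and the death never enters the Kaplan-Meier curve. In this illness a missed assessment followed by death is unlikely to be unrelated to prognosis, so the censoring would be informative and PFS would look better than it was. It also sits badly with a definition under which death from any cause ends PFS.

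**Working it through.** The SAP gives no figure to reproduce here, so the check applies each rule to one patient: death on treatment, after the first planned assessment date, no on-study assessment, no documented progression.

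| Rule | Applies? | Result |
|---|---|---|
| Section 7.1, no on-study assessment | Yes; its exception fails because the death came after the planned date | Censored at C1D1 |
| Table 4, "No on-study assessments" | Yes | Censored at C1D1 |
| Table 4, "Death prior to first planned tumor assessment" | No, the death came later | – |
| Table 4, "Death without objective progression prior to treatment discontinuation" | Yes; no prior assessment is required | Event at death |
| Table 4, "Death or progression after 2 or more missed tumor assessments" | Only once two assessments were missed | Censored at last assessment |
| Section 7.1, death within 28 days of discontinuation | No; needs at least one on-study assessment | – |
| Section 7.1, gap of more than 16 weeks | Runs from a previous assessment; this patient has none on study | – |

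After exactly one missed assessment, one rule (stated in the text and again in a table row) censors and one table row counts an event. After two or more, a further row points to censoring, while the event row still matches.

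**Effect on one patient.** The SAP's formula is event date − C1D1 + 1. Assume death on Day 40 with one assessment missed:

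- Censored at C1D1: 0 + 1 = 1 day, censored.
- Event at death: 39 + 1 = 40 days, event.

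**Who is in the analysis.** Section 9.2.2.1 answers this in two ways. Its text restricts efficacy to Safety Analysis Set patients in the expansion cohorts who have a baseline and at least one post-baseline disease assessment, which excludes this patient. Its Table 2 assigns PFS to the Per Protocol set in the expansion cohorts. That set, defined in Section 6.2, asks for a dose at the MTD level and no major Cycle 1 treatment deviation, but no post-baseline assessment. A patient with adequate Cycle 1 dosing who then dies unassessed can belong to it.

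**Illustration of size.** Assumptions, none from the SAP except that 30 is the upper size of an expansion cohort: 30 patients; 3 deaths of this kind before six months; 50% six-month PFS in the other 27; no other censoring.

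- Deaths censored at Day 1: (27 × 0.50) / 27 = 50%.
- Deaths counted: (27 × 0.50) / 30 = 13.5 / 30 = 45%.

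**The case against.** There is a fair case that this matters little.

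- **Population.** If the text of Section 9.2.2.1 governs, the patient is not in the PFS analysis and neither censoring rule affects the estimate. This stands, and it makes the bias conditional. It does not remove the conflict: Table 2 names a different set, and rules for patients without on-study assessments would have nobody to act on if all were excluded. Exclusion would also take these deaths out of PFS.
- **Specific over general.** Censoring rules always qualify a headline definition. One could read the Section 7.1 sentence as governing unassessed patients and the on-treatment death row as covering only assessed ones. That is possible, but the row does not say so.
- **Narrow class.** A missed marrow is not necessarily a missed assessment. Section 11.4 lets resistant disease be shown in blood and provides a treatment-failure category for some deaths without a marrow examination, so some of these patients may have an on-study entry. This narrows the class without emptying it; the SAP does not say whether such an entry counts as an assessment or as a PFS event.
- **Low stakes.** PFS is not among the endpoints in Sections 2.3.2 and 2.4, there are no hypotheses (Section 4.1), and overall survival is summarised as well. This stands and sets the severity.

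A reader might infer that the plan inflates PFS by five points or more, or that it discards unassessed deaths in general. The documents support neither. A death before the first planned assessment is an event under both Section 7.1 and Table 4. The five points come from an assumed count over six months, a longer window than the one in which only one assessment has been missed.

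**Conclusion.** The contradiction is real but minor. For a never-assessed patient who dies after the first planned assessment, on treatment or within 28 days of stopping, Section 7.1 and one Table 4 row censor at C1D1 while another row counts an event at death, and nothing ranks them. Following Section 7.1 drops an early death from an endpoint defined to include it.

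The upward bias in PFS is conditional on these patients being in the analysis set, as Table 2 allows and the text of Section 9.2.2.1 does not. Its size cannot be computed, because the SAP gives neither the assessment schedule nor an expected number of such deaths; 50% against 45% is an illustration only. PFS is a secondary, descriptive summary with no decision rule attached.

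**What to change.** 1. In Section 7.1 and Table 4, censor at C1D1 only when there is no on-study assessment or an inadequate baseline, **and** no death on treatment or within 28 days of discontinuation. Otherwise count an event at the date of death. The 28 days are already used in Section 7.1 and in footnote 2 to Table 4.
2. State in Table 4 that the on-treatment death row takes precedence over the rows for no on-study assessments and for inadequate baseline.
3. State how that row ranks against the row for two or more missed assessments when the patient was never assessed on study. Without this, later unassessed deaths would still match opposing rows.
4. Reconcile the text of Section 9.2.2.1 with its Table 2 so that these patients stay in the PFS analysis. Otherwise the first three changes may have no effect.

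Table 5 needs no matching change, because time to progression does not count death as an event. The cost is SAP wording only, best settled before results are known. PFS may become slightly less favourable.
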